### **6.3.5      *Adverse Event Reporting***

#### **Reporting Period**

Adverse events will be reported from the time of informed consent until study completion.

#### **Investigator Reporting: Notifying the Study Sponsor**

Every SAE, regardless of suspected causality (e.g., relationship to study product(s) or study procedure(s) or disease progression) must be reported to the sponsor within **24 hours** of learning of its occurrence.

Recurrent episodes, complications, or progression of the initial SAE must be reported to the Sponsor as a follow-up to the original episode within 24 hours of the investigator receiving the follow-up information. A SAE considered completely unrelated to a previously reported one should be reported separately as a new event.

New information regarding the SAE will be reported as it becomes available and in the same manner that the initial SAE (i.e. SAE form). The investigator must follow the event to resolution or until the event is deemed and documented irreversible, whichever is longer.

## **Investigator Reporting: Local Reporting Requirements**

The investigator will report AEs and SAEs to the IRB/EC of record and other local regulatory groups per the local requirements.

### **6.3.6     *Serious Adverse Event Reporting***

The study investigator shall complete an Unanticipated Adverse Device Effect Form and submit to the study sponsor and to the reviewing Institutional Review Board (IRB) . The study sponsor is responsible for conducting an evaluation of an unanticipated adverse device effect and shall report the results of such evaluation to the Food and Drug Administration (FDA) and to all reviewing IRBs and participating investigators per the applicable regulation.

## **6.4     *Unanticipated Problems***

### **6.4.1     *Definition of Unanticipated Problems (UP)***

The Office for Human Research Protections (OHRP) considers unanticipated problems involving risks to participants or others to include, in general, any incident, experience, or outcome that meets all the following criteria:

- Unexpected in terms of nature, severity, or frequency given (a) the research procedures that are described in the protocol-related documents, such as the Institutional Review Board (IRB)-approved research protocol and informed consent document; and (b) the characteristics of the participant population being studied;
- Related or possibly related to participation in the research (“possibly related” means there is a reasonable possibility that the incident, experience, or outcome may have been caused by the procedures involved in the research); and
- Suggests that the research places participants or others at a greater risk of harm (including physical, psychological, economic, or social harm) than was previously known or recognized.

### **6.4.2     *Unanticipated Problem Reporting***

Unanticipated problems (UPs) such as:

- Post-marketing withdrawal of a drug, device, or biologic used in a research protocol due to safety concerns.
- FDA ban of a drug, device, or biologic used in a research protocol due to safety concerns.
- Complaint of a participant when the complaint indicates unexpected risks, or the complaint cannot be resolved by the research team
- Breach of confidentiality
- Incarceration of a participant when the research was not previously approved under Subpart C and the investigator believes it is in the best interest of the subject to remain on the study
- Premature closure of a study (e.g., due safety, lack of efficacy, feasibility, financial reasons, etc.)

should be reported by the investigator to the Institutional Review Board (IRB). The UP report will include the following information:

- Protocol identifying information: protocol title and number, PI's name, and the IRB project number;
- A detailed description of the event, incident, experience, or outcome;
- An explanation of the basis for determining that the event, incident, experience, or outcome represents an UP;
- A description of any changes to the protocol or other corrective actions that have been taken or are proposed in response to the UP.

To satisfy the requirement for prompt reporting, UPs will be reported using the following timeline:

- UPs that are serious adverse events (SAEs) will be reported as any other SAE.
- Any other UP will be reported to the IRB 10 business days of the investigator becoming aware of the problem.
- All UPs should be reported to appropriate institutional officials (as required by an institution's written reporting procedures), the supporting agency head (or designee), and the Office for Human Research Protections (OHRP) within 10 business days of the IRB's receipt of the report of the problem from the investigator.

## 7 STATISTICAL CONSIDERATIONS

### 7.1 Statistical Hypotheses

- Primary Efficacy Endpoint(s): We anticipate anatomic correlation between CT identified epicardial adipose tissue within 3 pixels ( $0.625 \times 3 = 1.875\text{mm}$ ) of an endocardial mapping point where HFS confirmed a vagal response consistent with ganglionated plexus innervation.
- Secondary Efficacy Endpoint(s): Acute procedural success defined by elimination of ear vagus nerve stimulation response will be achievable in all patients.

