## 1 STUDY SUMMARY

### 1.1 Synopsis

**Title:** PROSPECTIVE EVALUATION OF COMPUTED TOMOGRAPHY GUIDED MAPPING AND ABLATION OF CARDIAC GANGLIONATED PLEXI IN PATIENTS WITH ATRIAL FIBRILLATION

**Short Title:** CT Guided Ablation of Ganglionated Plexi

**Study Description:** Single-arm prospective study to evaluate the role of high frequency stimulation (HFS) and computed tomography (CT) guided mapping and ablation of ganglionated plexi (GP) in patients with atrial fibrillation.

**Objectives:** Primary:

Secondary:

To assess the effects of GP ablation on local HFS response and global vagal stimulation in order to characterize the neural pathways connecting GPs

**Primary Endpoint:** The primary outcome of interest will be the successful identification of GP signals by high frequency stimulation and anatomic correlation between these points and CT identified epicardial adipose tissue within 3 pixels ( $0.625 \times 3 = 1.875$ mm).

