### 2.2 Background

Autonomic cardiac innervation arises from the brainstem and travels to the heart via the cervical and thoracic stellate ganglion (sympathetic system) and the vagus nerve (parasympathetic system). The two systems combine to innervate the heart in a dense network of post-ganglionic axons called the ganglionated plexi (Hou Y, et al). These ganglionated plexi are located at the base of the heart in the epicardial adipose tissue (Goudis CA, et al; Armour JA, et al).

With direct visualization of the epicardial adipose tissue at the time of cardiac surgery, autonomic modulation with injection of botulinum toxin has been shown to reduce short and long term burden of atrial fibrillation (Romanov A et al; Waldron et al). Several techniques have been proposed to identify the ganglionated plexi at the time of endocardial procedures. Anatomic approaches have been utilized targeting classical regions of autonomic innervation, although this procedure has several limitations including individual anatomic

variation. In addition, high frequency stimulation mapping to identify local vagal responses has been used (Kim MY, et al; Hu F, et al). This technique is limited by the need for general anesthesia and the duration of time required to map the entire atrium, which is especially relevant for non-atrial fibrillation ablation procedures where such mapping would not otherwise be required. More recently, techniques to evaluate local electrograms have been developed based on the principle that fractionated electrical activity may be noted in the endocardium beneath ganglionated plexi due to the inter-myocardial nerve fibers that interrupt normal myocardial-to-myocardial conduction (Pachon M JC, et al; Lellouche N, et al).

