### 3 STUDY OBJECTIVES AND ENDPOINTS

OBJECTIVES	ENDPOINTS	JUSTIFICATION FOR ENDPOINTS
Primary		
	
 
Successful identification of GP signals by high frequency stimulation and anatomic correlation between these points and CT identified epicardial adipose tissue within 3 pixels (0.625x3=1.875mm).
 
	This correlation will allow us to determine the ability of pre-procedural CT imaging to predict GP location.
Secondary		
To assess the effects of GP ablation on local HFS response and global vagal stimulation in order to characterize the neural pathways connecting GPs	
 
Elimination of local of HFS response following GP ablation
 
Elimination of global vagal response to non-invasive ear stimulation
 
	
	
 
Amplitude, duration, and fractionation of signals at sites with HFS responses and successful HFS elimination
 
	

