#### 7.2.2 *Analysis of the Primary Efficacy Endpoint(s)*

- Anatomic correlation between CT and GP mapping will be defined based on review of electroanatomic maps from the ablation procedure merged with segmented pre-procedural CT images.

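### The primary endpoint scores CT–HFS agreement yes/no at one 1.875 mm cut-off, with no measuring rule, continuous distance, merge-error record, other tolerance or HFS-negative comparison, so the rate is hard to interpret

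*Combined protocol and SAP*

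**What the plan says.** The same distance criterion appears in three places. The Synopsis (1.1) defines the primary outcome as identification of GP signals by HFS and "anatomic correlation between these points and CT identified epicardial adipose tissue within 3 pixels". The table in section 3 repeats the limit, "within 3 pixels (0.625x3=1.875mm", and gives its purpose: to show whether pre-procedural CT can predict where the GPs are. Section 7.1 anticipates "anatomic correlation between CT identified epicardial adipose tissue within 3 pixels" and names the two ends of the distance: CT-identified epicardial fat, and a site described by the words "of an endocardial mapping point where HFS confirmed a vagal response consistent with ganglionated plexus innervation".

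Section 7.2.2 is the whole primary analysis. It says agreement is defined by reviewing "electroanatomic maps from the ablation procedure merged with segmented pre-procedural CT images". It does not say how the distance is taken on the merged image.

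Section 2.2 places the two ends on different layers. On the plexi it says: "These ganglionated plexi are located at the base of the heart in the epicardial adipose tissue". On local electrograms it says: "fractionated electrical activity may be noted in the endocardium beneath ganglionated plexi".

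The plan contains no second tolerance, no distance analysed as a number, no accuracy record or limit for the merge, and no comparison with sites where HFS drew no response. Section 7.2.1 summarises continuous data by medians, but distance is nowhere named as a variable.

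**The concern.** The quantity of interest is a distance, and the plan keeps only whether it falls below one limit. If it is measured straight from the endocardial point to epicardial fat, it includes the wall between them. However it is measured, it includes the error of aligning the map to the CT.

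These errors act in both directions. A point directly under fat can be scored a miss, and a point with fat nearby but not over it can be scored a match. With no HFS-negative points for comparison, the plan also cannot show how often a match would arise wherever the catheter happened to be.

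A low rate could therefore mean that CT does not locate GPs, or that the tolerance is small relative to the measurement error. A high rate could mean that CT works, or that fat lies close to most stimulated sites. With 19 patients at one center and no other primary analysis, nothing else in the plan resolves this.

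**Working it through.** **The plan's own figure.** 3 × 0.625 mm = 1.875 mm, which reproduces exactly. On the same scale, 4 pixels = 2.5 mm, 5 pixels = 3.125 mm and 8 pixels = 5.0 mm. The documents give no power or precision calculation for this endpoint to reproduce.

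**Inputs.** The cut-off T = 1.875 mm comes from sections 1.1, 3 and 7.1. Wall thickness w and merge-error SD s are not in the documents; both are assumptions.

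**Model for a true match.** Fat lies directly over the point. Measured distance = w + e, with e ~ Normal(0, s) along the line through the wall. The chance of being scored a match is Φ((T − w)/s).

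With s = 1 mm:
- w = 1, T = 1.875: Φ(0.875) = 81%
- w = 2, T = 1.875: Φ(−0.125) = 45%
- w = 2, T = 2.5: Φ(0.5) = 69%

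Other values at T = 1.875 mm:

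| w (mm) | s = 0.5 | s = 1 | s = 2 | s = 3 |
|---|---|---|---|---|
| 0.5 | 99.7% | 92% | 75% | 68% |
| 1 | 96% | 81% | 67% | 62% |
| 2 | 40% | 45% | 48% | 48% |
| 3 | 1% | 13% | 29% | 35% |

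Under this model, once w exceeds 1.875 mm fewer than half of true matches are counted, whatever s is.

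**Sensitivity to the model.** A version that also scores a miss when error carries the point more than 1.875 mm past the fat edge uses P(|w + e| < T). At w = 1, s = 1 this is Φ(0.875) − Φ(−2.875) = 0.809 − 0.002 = 81%; at w = 2, s = 1 it remains 45%. The two versions part at larger error: at w = 1, s = 2 they give 67% and 59%. A three-dimensional simulation that allows sideways error (fat patch of radius 2 or 4 mm, 3 mm thick, 400,000 draws) gives 81% and 44–45% at s = 1 for w = 1 and 2. At s = 2 it gives 54–65% and 38–46%.

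**The opposite error.** Suppose fat is beside the point, at a true distance of 3 mm, with s = 1 mm. The same formula counts it as a match in Φ(−1.125) = 13% at 1.875 mm, Φ(0.125) = 55% at 3.125 mm and Φ(2) = 98% at 5.0 mm. Wider tolerances recover true matches (w = 2, s = 1: 87% at 3.125 mm, 99.9% at 5.0 mm) but admit others too. They are informative only if applied to HFS-negative points as well.

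**The case against.** The strongest objection is that the wall term is not established. Section 7.2.2 does not say which CT surfaces are segmented or whether points are projected across the wall before measuring. A reader might infer from section 7.1 that the distance always contains the wall, but that rests on a literal reading the plan neither confirms nor excludes. This stands. If points are projected, w = 0 and at s = 1 mm the match rate is 94% or 97%, depending on the model. Merge error, the single threshold and the missing comparison remain, and the silence is itself a gap.

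Other tempting readings go too far:
- **A very wide range of rates.** Pairing w = 0, s = 1 with w = 3, s = 1 would suggest one true relationship could read as anything from 94% to 13%. Those are corners of an assumed grid, and the first needs no wall at all.
- **A cut-off that is simply too tight.** Error can also create matches, so the net direction is unknown.
- **A limit chosen from image resolution alone.** The plan gives no reason for 3 pixels. Three rather than one may already be an allowance for error.
- **An ambiguous unit.** The millimetre value is printed wherever the limit is stated.

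It is also fair to say that one fixed cut-off in a small observational feasibility study prevents choosing a threshold after seeing the data. That is a reason to keep 1.875 mm as primary. It is no reason to omit the underlying distance and a short list fixed in advance.

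**Conclusion.** The concern holds as one of interpretation. The documents support this much: one yes/no limit, an endocardial point compared with epicardial fat on a merged image, and no measuring rule, continuous distance, merge-error record, other tolerance or HFS-negative comparison. On that basis the agreement rate cannot by itself answer the question set in section 3.

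The size is illustrative. At an assumed merge-error SD of 1 mm, the share of true matches counted falls from about 81% to 45% as the assumed wall goes from 1 to 2 mm, and one extra pixel moves 45% to 69%. These figures are stable across the three models tried at that SD and less so at 2 mm. They show that the result could depend materially on the threshold; they do not predict this trial's rate. The documents do not support calling the 1.875 mm limit wrong or the endpoint biased in a known direction.

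**What to change.** Keep 1.875 mm as the primary cut-off and add to section 7.2.2:

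1. How the distance is measured: directly from the endocardial point, or after projection across the wall.
2. The continuous distance to the nearest CT fat for every stimulated point, compared within patient between HFS-positive and HFS-negative points. One simple form is each patient's difference in median distance, summarised over the 19 patients. HFS status should come from baseline mapping, because section 4.8.1 repeats HFS after each ablation and a response lost then does not make a site HFS-negative.
3. Agreement at pre-listed wider tolerances, for example 5 and 8 pixel-equivalents (3.125 and 5.0 mm), applied equally to HFS-positive and HFS-negative points.
4. The merge error for each case.

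The cost is small but not only wording. Section 4.8.1 stimulates for up to 10 seconds or until a response, so non-responding sites should arise, but nothing says their locations are kept. They must be saved, distances must be extracted from the merged maps, and a few more figures reported. No added patient procedure is needed, and fixing the list in advance avoids a post-hoc choice of threshold.

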**Secondary Endpoints:**

[figure not shown]
- Elimination of local of HFS response following GP ablation
- Elimination of global vagal response to non-invasive ear stimulation
- Characterization of amplitude, duration, and fractionation of signals at sites with HFS responses and successful HFS elimination

**Study Population:** 19 patients with atrial fibrillation undergoing catheter ablation of atrial fibrillation

**Description of Sites/Facilities** All ablation procedures will be performed at the Hospital of the University of Pennsylvania.

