## **STUDY POPULATION**

### **4.4 Inclusion Criteria**

In order to be eligible to participate in this study, an individual must meet all of the following criteria:

1. Provision of signed and dated informed consent form
2. Stated willingness to comply with all study procedures and availability for the duration of the study
3. Male or female, aged >18 years
4. History of AF with plan to undergo catheter ablation

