### **4.5 Exclusion Criteria**

An individual who meets any of the following criteria will be excluded from participation in this study:

1. Contraindication or unwillingness to undergo CT imaging or catheter ablation.
2. Pregnancy or lactation

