## STUDY INTERVENTION

### 4.8 Study Intervention(s) Administration

#### 4.8.1 *Study Intervention Description*

All patients will have GP mapping performed using the Nicolet (Natus) Cortical Stimulator (see attached) with 12V output at 20Hz frequency with 10ms pulse duration with at least 3grams of contact force. Stimulation will be provided for up to 10 seconds or until vagal response is noted (>2s ventricular asystole, AV block, or R-R interval increase by at least 50%). Natus stimulator had FDA clearance (K072964) for cortical stimulation. Prior to ablation, baseline ear vagus nerve stimulation will be performed via stimulation of bilateral cyma concha to document response using Parasym tragal stimulator (IDE information attached). Ablation of mapped GPs will be performed using standard ablation catheter with routine approaches to ablation energy delivery and monitoring (see below flowchart). Following ablation of each GP, local HFS will be repeated in all GP regions and ear vagus nerve stimulation will be repeated via bilateral cyma concha. After all GP are ablated, all patients be given IV atropine (0.04mg/kg max: 4mg) to assess global vagal tone. Following this, patients will undergo pulmonary vein isolation using standard equipment and techniques.

Devices will be obtained from the manufacturer (Natus and Parasym respectively) and will be stored in a secured laboratory space. No particular temperature or climate requirements are present for either device. All devices will be labeled according to the manufacturer guidance and will be returned to the manufacturer in the event of any device failure. Devices will be stored and managed in compliance with OCR guidelines.

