## 6 STUDY ASSESSMENT AND PROCEDURES

### 6.1 Efficacy Assessments

- Elimination of local HFS response and ear vagus nerve stimulation will determine acute procedural efficacy
- Loop recorder or ambulatory monitors interrogations to evaluate presence and burden of atrial fibrillation
- History to identify symptomatic atrial fibrillation and to identify episodes of AF that may have been vagally mediated

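### Do the two descriptions of acute procedural success, and the unstated denominator for the ear response, call for a change to the plan?

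*Combined protocol and SAP*

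**What the plan says.** Section 7.1 gives one secondary hypothesis: "Acute procedural success defined by elimination of ear vagus nerve stimulation response will be achievable in all patients". Section 6.1, under efficacy assessments, says "Elimination of local HFS response and ear vagus nerve stimulation will determine acute procedural efficacy", and then lists rhythm monitoring and clinical history.

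The synopsis and the Section 3 table each carry two separate secondary endpoints, "Elimination of local of HFS response following GP ablation" and "Elimination of global vagal response to non-invasive ear stimulation". Neither place combines them.

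The disease criterion for entry is "History of AF with plan to undergo catheter ablation". Nothing else in Sections 4.4 and 4.5 concerns an ear response. Section 4.8.1 says that before ablation "baseline ear vagus nerve stimulation will be performed via stimulation of bilateral cyma concha to document response", and that HFS and ear stimulation are both repeated after each ganglionated plexus (GP) is ablated. It refers to a flowchart that is not shown in the text available.

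Section 7.2.1 provides for percentages for categorical data. Section 7.2.3, on secondary endpoints, speaks only of AF burden.

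**The concern.** Two things look wrong. First, 7.1 rests success on the ear response alone, while 6.1 brings in the HFS response. A patient who loses the ear response but keeps an HFS response at some site is a success under 7.1 and has no clear status under 6.1.

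Second, 7.1 speaks of every patient, yet patients may enter without any ear response to eliminate. Such a patient could be counted as a success (no response after ablation), as a failure (nothing was eliminated), or left out. With 19 patients, each one moves the rate by 1/19 = 5.3 percentage points. If the rule were chosen after the results were known, the most favourable count could be reported.

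**Working it through.** The plan states no rate, power or sample-size figure for this outcome, so there is none to reproduce. The check is a comparison of the texts, followed by an illustration of how far the counting rule could matter.

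**Definition.**

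- Section 7.1 is the only place that defines acute procedural success, and it does so by the ear response.
- Section 6.1 uses a different term, efficacy, in a list of what is assessed. It does not say that a patient must meet both conditions.
- The synopsis and Section 3 report the two eliminations as separate endpoints.

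These fit together: both responses are assessed acutely, each is its own endpoint, and the hypothesis is stated for the ear response. A composite appears nowhere. If one were imposed, with all 19 patients losing the ear response and j keeping an HFS response, the rate would be (19 − j)/19. For an assumed j = 2 that is 17/19 = 89.5% (exact 95% CI 66.9–98.7%), against 19/19 under 7.1. That contrast depends on a rule the plan does not contain.

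**Denominator.** Inputs: N = 19 (synopsis); k = patients without a baseline ear response (assumed, since the documents give no rate); every responder is taken to lose the response. Intervals are Clopper–Pearson. For m/m the lower limit is 0.025^(1/m): 0.8235 for m = 19, 0.8049 for m = 17 and 0.7820 for m = 15.

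| k | Counted as successes | Excluded: (19 − k)/(19 − k) | Counted as failures: (19 − k)/19 |
|---|---|---|---|
| 0 | 19/19 (82.4–100%) | 19/19 (82.4–100%) | 19/19 (82.4–100%) |
| 2 | 19/19 (82.4–100%) | 17/17 (80.5–100%) | 17/19 = 89.5% (66.9–98.7%) |
| 4 | 19/19 (82.4–100%) | 15/15 (78.2–100%) | 15/19 = 78.9% (54.4–93.9%) |

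The spread is nil at k = 0 and grows with k. The three columns are not equally plausible, however. Elimination presupposes something to eliminate, so the middle column is the ordinary meaning of the endpoint. The baseline test identifies that group before any ablation, so membership does not depend on the outcome.

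**Smaller gaps.** Section 4.8.1 gives the criterion for a vagal response in the sentence on HFS mapping (a ventricular pause longer than 2 s, AV block, or R-R lengthening of at least 50%). Section 3 uses the same term for ear stimulation, so applying the criterion there is a reasonable reading, though not a stated one. Testing is repeated after each GP, and the test after the last GP is the natural one to decide the outcome. The flowchart may settle this, and it may also address non-responders.

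**The case for a change.** The strongest case for a change is that this is the only secondary hypothesis stated, in a small single-arm study, and that the section meant to describe its analysis does not mention it. The counting rule can matter more than the table shows when conversion is incomplete. Assume 13 baseline responders, of whom 9 lose the response. The rate is 9/13 = 69.2% (38.6–90.9%) among responders, 9/19 = 47.4% (24.4–71.1%) if the 6 non-responders count as failures, and (9 + 6)/19 = 78.9% (54.4–93.9%) if they count as successes. It can also be said that leaving non-responders out is itself a departure from the literal wording of 7.1, and that one sentence written in advance would cost nothing.

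Part of this stands. The denominator is unwritten in the text available, 7.2.3 gives no analysis for either elimination endpoint, and the phrase about all patients is loose. But that phrase states an expectation. It names no analysis set, and no test or threshold is attached to it. The wide contrasts come from assumed inputs and from two counting rules that fit poorly with the meaning of elimination. The baseline and repeat responses called for in 4.8.1 would let a reader recompute any version.

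**Conclusion.** The plan can stand. Sections 6.1 and 7.1 differ in emphasis but do not conflict once the separate endpoints in the synopsis and Section 3 are read with them. What remains is missing detail on how a descriptive secondary percentage is counted. A competent analyst would fill it from data the protocol already collects: ear elimination among patients with a documented baseline response, the number without one reported, and HFS elimination reported separately.

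The effect on the reported rate cannot be determined from the documents. It is nil if all 19 patients respond at baseline, and in the illustrations it reaches tens of percentage points only under counting rules that the ordinary meaning does not support. No inference or trial decision is tied to the result, and the primary endpoint, the match between HFS sites and epicardial fat on CT, does not use the ear response. An exact interval or a patient-level HFS rule would be an optional refinement; the plan as it stands does not depend on either.

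This rests on two assumptions: that the baseline ear response is recorded as 4.8.1 requires, and that the flowchart not shown contains no contrary counting rule.

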### **4.2 Scientific Rationale for Study Design**

This study is designed to characterize the association between CT identified epicardial adipose tissue and HFS mapping identified GP sites in the right and left atrium. Given the evidence that GP ablation can be beneficial for patients undergoing catheter ablation for atrial fibrillation, all patients will undergo GP ablation following mapping in addition to standard pulmonary vein isolation. The hierarchical relationship within the network of cardiac GPs is unknown as is the optimal order of GP ablation. Given equipoise in the order of GP ablation, we will equally allocate the site of initial ablation between the 8 major GP ablation locations.

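### The ear-stimulation endpoint is a yes/no with no time point, expected in every patient; as a final result it cannot separate first-ablation sites, and section 7 states no analysis of the repeated ear tests.

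*Combined protocol and SAP*

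**What the plan says.** - **Order question.** Section 4.2: "The hierarchical relationship within the network of cardiac GPs is unknown as is the optimal order of GP ablation". For that reason, "we will equally allocate the site of initial ablation between the 8 major GP ablation locations". The secondary objective in section 3 is to learn about the pathways that connect the GPs.
- **Measurement.** Section 4.8.1: "Prior to ablation, baseline ear vagus nerve stimulation will be performed", and then "Following ablation of each GP, local HFS will be repeated in all GP regions and ear vagus nerve stimulation will be repeated". The readable text thus provides one ear test at baseline and one after every GP.
- **Endpoint.** Section 3 lists "Elimination of global vagal response to non-invasive ear stimulation". It gives no time point, no count of steps and no criterion for an ear response.
- **Hypothesis.** Section 7.1: "Acute procedural success defined by elimination of ear vagus nerve stimulation response will be achievable in all patients".
- **Analysis.** Section 7.2.3, on the secondary endpoints, covers AF burden only. No readable text in section 7 mentions the allocated first site, the order of ablation or the ear tests after each step.

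**The concern.** The objective, the allocation of the first site and the repeated testing all concern order and network. The stated endpoint and hypothesis keep one binary fact per patient and expect it to be positive in everyone.

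Sections 4.2 and 4.8.1 have every patient undergo ablation of the mapped GPs, so the natural patient-level reading is the state at the end of the sequence. By then the site that came first has been joined by the others. A result at or near its ceiling in every first-site group says nothing about which GP carries the global vagal response.

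If the repeated tests are left without a stated summary, the order question will be answered by a summary chosen after the data are seen, or not at all.

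**Working it through.** The plan gives no power, effect size or expected rate other than all patients, so there is no figure of its own to reproduce. Inputs from the documents: 19 patients (section 1.1), 8 first sites (4.2), an ear test after each GP (4.8.1), two-sided tests at 0.05 (7.2.1).

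1. **Allocation.** 19/8 = 2.375, so the most even split is three sites with 3 patients and five with 2 (3 × 3 + 5 × 2 = 19).

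2. **Final yes/no if the hypothesis holds.** One site against the rest is 3/3 against 16/16: Fisher p = 1. There is no variation to analyse.

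3. **Precision of the final yes/no.** The two-sided 95% exact lower limit for 19/19 is 0.025^(1/19) = 0.824. All 19 would succeed with probability 0.90^19 = 0.14, 0.95^19 = 0.38 or 0.98^19 = 0.68 at assumed true rates of 90%, 95% and 98%.

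4. **Final yes/no short of 100%.** Assume that one gateway GP abolishes the response with probability 0.8 when ablated and each of the other seven with 0.1, independently and permanently. Final elimination is 1 − 0.2 × 0.9^7 = 0.904 in any order. This follows from the assumptions; it shows that the argument does not need an exact ceiling.

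5. **What the step-wise tests could add.** If all 8 GPs are ablated in all 19 patients, there are 19 × 8 = 152 ear tests after ablation. Trials were simulated under the model in step 4, with 19 baseline responders, the later sites in random order and 2 or 3 patients per first site:
   - Mean steps to elimination are 1.4 (gateway first) against 4.0 (other site first) among patients who reach elimination. Scoring the never-eliminated as 9 gives 0.904 × 1.4 + 0.096 × 9 = 2.1 against 0.904 × 4.0 + 0.096 × 9 = 4.5 (4.4 without rounding the mean).
   - The pooled rate per GP (eliminations divided by ablations done while the response was present) is highest for the gateway in over 99% of trials. At 0.5 against 0.15 this is about 86%, and about 74% with 12 responders. Guessing gives 1/8 = 12.5%.
   - Fewest mean steps by allocated first site, with the never-eliminated scored 9, finds the gateway in only about two thirds of trials (0.8/0.1) or one third (0.5/0.15).
   - With no gateway (every GP at 0.2), the top GP's rate is still at least twice the median rate in 47–48% of trials.

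6. **Limits of testing by first site.** The smallest possible two-sided Fisher p between two sites is 2/C(6,3) = 0.10 (3 v 3), 1/C(5,2) = 0.10 (2 v 3) or 2/C(4,2) = 0.33 (2 v 2). One site against the rest can reach 1/C(19,3) = 0.001. Its power for elimination after the first GP, 3 v 16, is:

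| Assumed rates | α = 0.05 | α = 0.05/8 |
|---|---|---|
| 80% v 10% | 0.57 | 0.26 |
| 80% v 20% | 0.42 | 0.07 |
| 90% v 10% | 0.76 | 0.38 |

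A global eight-group permutation test on steps has power of about 0.46 even in an assumed strong case (gateway first: 1–2 steps; other sites first: 3–8).

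**The case against.** A reader might infer that the plan fixes the ear endpoint once all GPs are ablated. It does not: in section 4.8.1 that timing belongs to another test, "After all GP are ablated, all patients be given IV atropine". The endpoint simply has no time point, and end of sequence is one reading of it. This stands, but an endpoint without a time point needs the same repair.

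A reader might also infer that the study cannot inform order at all. That goes too far. The ear tests after each GP are collected, and local HFS is repeated in all GP regions after each GP, which is arguably the more direct view of the network. The 7.1 statement is an expectation of acute success and does not claim to answer the order question. The flowchart cited in section 4.8.1 is not visible and may say more about the sequence.

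The simulation assumes a gateway and then finds it, with independent and permanent effects. It shows what the step-wise data could carry under those assumptions, not what they will show. Its best figures belong to the pooled rate per GP and not to the comparison by first site. The no-gateway case shows that a top-ranked GP can easily arise by chance.

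Finally, this is a secondary endpoint in a 19-patient, single-arm study described as observational and concerned with feasibility. That limits the weight of the point, but not the case for stating the summary in advance.

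**Conclusion.** The point holds in a limited form. As a patient-level final result, the ear endpoint cannot distinguish first sites. Under the plan's own hypothesis it has no variation at all, and under the independent-effects model its expected value is the same in any order. No readable text in section 7 says how the repeated ear tests will be summarised by step or by first site.

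The loss lies in the analysis and not in the data: up to 152 planned ear tests are reduced to 19 binary results. The documents do not support saying that the study learns nothing about order, or that a step-wise analysis would identify a controlling GP reliably. All elimination rates used here are assumptions, because the documents give none. With 2 or 3 patients per first site, whatever is reported on order is exploratory.

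**What to change.** In sections 7.1 and 7.2.3:

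1. State the criterion for an ear response in advance. The vagal-response threshold in 4.8.1 is written for HFS mapping. Restrict the ear analysis to patients who meet the criterion at baseline, and report how many do not.
2. Make the main ear analysis the ablation step at which the response is first absent and stays absent at all later retests. Censor patients never eliminated at their last step.
3. For each GP, report the number of ablations that eliminated the response divided by the number done while it was still present, with an exact confidence interval.
4. List steps to elimination by allocated first site, without site-to-site tests.
5. Label items 3 and 4 descriptive and exploratory, and say that the highest observed rate can arise by chance.
6. Keep the final yes/no as a descriptive line with its time point and exact interval (a lower limit of 82.4% if 19 of 19 respond at baseline and are eliminated).

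The cost is a small amount of extra analysis, a definition to agree before the data are seen, and a less definitive conclusion on order. No extra procedure or patient is needed, because the retests are already planned.
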